3.5. Sample Size and Power Estimation

A sample size of 420 patients allows to estimate the mean of a specific component of TSQM-9 at Day 57 with a precision (half width) of the 95% confidence interval (CI) ranging from ± 1.6 to ± 2.1 if we assume a standard deviation between 15 and 20.

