8.1 Number of Patients

The study will enroll approximately 420 patients with AK of the face and scalp. Approximately, 350 patients in Spain (35 sites) and 70 patients in Italy (7 sites) are expected to be enrolled.

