11.1 Sample size Calculation

A total of 420 patients will be enrolled in the trial. A sample size of 420 patients allows to estimate the mean of a specific component of TSQM-9 at Day 57 with a precision of the 95% confidence interval (CI) ranging from ± 1.6 to ± 2.1 and assuming a standard deviation between 15 and 20.²² Screening failures will not be replaced. Drop-outs will not be replaced

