1. INTRODUCTION

The current Statistical Analysis Plan (SAP) for the Final Analyses refers to Clinical Trial Protocol Version 3.0 for Spain dated March 21st, 2023 and Clinical Trial Protocol Version 2.0 for Italy dated March 21st, 2023.

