4.4.3. Handling of Drop-Out Patients

Screening failure patients and drop-out patients will not be replaced in this study.

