5. ANALYSIS POPULATIONS

Starting from Screened patients (i.e., all patients who signed the informed consent form), the following analysis populations will be defined for statistical analysis:

- **Enrolled population:** all patients who signed the informed consent form and completed the screening disposition.
- **Full analysis set (FAS) population:** all patients who signed the informed consent form and applied at least one dose of Tirbanibulin.
- **Evaluable patient population:** FAS patients who completed the 57 days of observation and have the TSQM-9 assessment.
- **Safety patient population:** Full analysis set patients.
- **LC-OCT Population:** FAS patients who performed at least one valid LC-OCT assessment (i.e., FAS patients enrolled at site 101).

	Statistical Analysis Plan Sponsor: ALMIRALL, S.A. Protocol number: M-14789-42
---	--

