If item9 missing	$\frac{(\sum \text{the 2 completed items}) - 2}{8} * 100$

If more than one item is missing from a domain of the TSQM-9 for a particular patient, this domain should be considered invalid for that respondent.

Analysis methodology

All the analysis on TSQM-9 questionnaire will be provided by country, by AK lesion localization (i.e., face and scalp) and overall.

Considering only the answers to the questions 1 to 3 and 9 to 14 (i.e. excluding the 5 questions related to side effects in TSQM 1.4 eCRF page) provided by the patients at Day 57, a first summary of patients who completed the questionnaire (i.e., patients with no more of one missing answer for each component) will be provided, while the total sub-scores computed as explained above, will be described.

	Statistical Analysis Plan Sponsor: ALMIRALL, S.A. Protocol number: M-14789-42
---	--

In advance, 95% CI for mean value of Convenience, Efficacy and Total Satisfaction items' scores at day 57 will be estimated using Student's t distribution, regardless response's distribution.

Moreover, the proportion of patients for each answer at questions of TSQM-9 questionnaire will be provided.

Data handling rules

No missing imputation will be performed.

Sensitivity of primary analysis

Not applicable.

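### 420 analysed patients give a 95% CI half-width of ±1.4 to ±1.9, not the stated ±1.6 to ±2.1, and the plan states no loss allowance that would explain the difference

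*SAP*

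**What the plan says.** SAP 3.5 links a sample of 420 patients to a 95% CI half-width for the mean of one TSQM-9 component at Day 57 "ranging from ± 1.6 to ± 2.1 if we assume a standard deviation between 15 and 20". The Protocol synopsis gives the same statement. Protocol 11.1 repeats it as "ranging from ± 1.6 to ± 2.1 and assuming a standard deviation between 15 and 20" and adds that 420 is the number to be enrolled.

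Four other provisions bear on the figure:

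- **Interval method.** SAP 6.3.1 plans a "95% CI for mean value of Convenience, Efficacy and Total Satisfaction" scores, computed with Student's t whatever the shape of the distribution. SAP 4.1 sets a two-sided alpha of 0.05.
- **Who is analysed.** The primary analysis uses the Evaluable population, defined in SAP 5 as "FAS patients who completed the 57 days of observation and have the TSQM-9 assessment".
- **Losses.** SAP 4.4.3: "Screening failure patients and drop-out patients will not be replaced in this study". Protocol 11.1 agrees. Neither document gives a loss rate or a target number of Evaluable patients.
- **Who is enrolled.** In Protocol 11.2 the Enrolled population is everyone who signed consent. In SAP 5 it is "all patients who signed the informed consent form and completed the screening disposition".

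**The concern.** All the inputs to the precision statement are printed, so it can be checked directly, and 420 patients do not produce the printed half-widths. Both ends are too wide, by about the same proportion, which suggests that a smaller number or an unstated inflation lies behind them.

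The trial is single-arm and descriptive, with no hypothesis test and no power calculation. This sentence is therefore the whole quantitative case for the sample size. As it stands, a reader cannot tell whether the sponsor planned for about 350 analysed patients out of 420, expected all 420 to be analysed and miscalculated, or did something else. The precision the trial is meant to deliver in its Evaluable population cannot be verified.

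**Working it through.** **Inputs.** n = 420, SD 15 and 20, 95% two-sided (SAP 3.5, SAP 4.1, Protocol 11.1); Student's t interval (SAP 6.3.1).

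**Formula.** Half-width = q × SD / √n, where q is 1.96 (normal) or the 97.5% point of t with n − 1 degrees of freedom.

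**Attempt to reproduce the stated figure at n = 420** (√420 = 20.494):

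- Normal: 1.96 × 15 / 20.494 = 1.43; 1.96 × 20 / 20.494 = 1.91.
- Student's t, 419 df: 1.439 and 1.918.
- Stated: 1.6 and 2.1.

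The ratio of stated to computed (t) is 1.6 / 1.439 = 1.11 and 2.1 / 1.918 = 1.09. The differences are 0.16 and 0.18 points. The printed values have one decimal, so the excess could lie anywhere from 1.55 − 1.439 = 0.11 to 2.15 − 1.918 = 0.23 points. Rounding alone cannot close the gap. To obtain 1.6 and 2.1 from 420 patients, the SDs would have to be about 16.7 and 22.0.

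**Other constructions at n = 420:**

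| Construction | SD 15 | SD 20 | Rounds to 1.6 / 2.1? |
|---|---|---|---|
| 90% CI | 1.20 | 1.61 | no |
| 97.5% CI | 1.64 | 2.19 | no |
| 99% CI | 1.89 | 2.51 | no |
| Bonferroni over 3 domains | 1.75 | 2.34 | no |
| Median, under normality | 1.80 | 2.40 | no |
| Half-width not exceeded with 95% probability | 1.52 | 2.03 | no |
| Half-width not exceeded with 99% probability | 1.555 | 2.073 | yes |
| Design effect, assumed ICC 0.02, 10 patients per site | 1.558 | 2.078 | yes |

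The documents mention neither of the two that match.

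**Which n fits the printed pair?** Requiring SD 15 to round to 1.6 and SD 20 to round to 2.1:

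- Student's t: n = 335 to 362, which is 20.2% to 13.8% below 420.
- Normal: n = 333 to 359, which is 20.7% to 14.5% below 420.

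**Half-width by loss from 420 (Student's t; the loss rates are illustrative, as the documents give none):**

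| Not evaluable | n analysed | SD 15 | SD 20 |
|---|---|---|---|
| 0% | 420 | ±1.44 | ±1.92 |
| 5% | 399 | ±1.48 | ±1.97 |
| 10% | 378 | ±1.52 | ±2.02 |
| 15% | 357 | ±1.56 | ±2.08 |
| about 17% | 350 | ±1.58 | ±2.10 |
| 20% | 336 | ±1.61 | ±2.15 |

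**Smallest n that meets the printed limits without rounding (t).** A half-width of at most 1.60 at SD 15 needs 341; at most 2.10 at SD 20 needs 351. Both hold with 351 or more, so up to 420 − 351 = 69 patients (16.4%) could be non-evaluable.

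**The case against.** The strongest reply is that this is harmless. The error is on the safe side: unless more than about 16% of 420 are lost, precision will be at least as good as stated. The reported interval will use the observed SD and n, nothing is tested, and the interim analysis has already been done. All of that is true and limits the point to a correction of the record. It does not make the sentence correct, and nothing in either document allows a reader to judge whether losses will stay below that level.

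A second reply is that a drop-out allowance, or a design effect for clustering by site, was simply understood. The Protocol does plan at least 10 patients per site, and an ICC near 0.02 would give the printed pair. But the sentence ties the precision to 420 patients, and no ICC, design effect or loss rate is mentioned. A planning number of 350 would also fit and happens to equal the Spanish recruitment target in Protocol 8.1, but the documents do not make that link. A smaller n is one possible origin, not an established one.

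A third reply concerns the remedy. Writing a loss rate of about 17% into a SAP issued after the interim would present a back-calculated number as a planning assumption. That caution stands, and the fix must respect it.

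The difference in the Enrolled definition may be a version effect. The SAP follows "Clinical Trial Protocol Version 3.0 for Spain dated March 21st, 2023" and version 2.0 for Italy, whereas the Protocol available here is version 1.0. The arithmetic does not depend on it.

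**Conclusion.** The concern holds. For 420 analysed patients the 95% half-width is ±1.4 (SD 15) to ±1.9 (SD 20); the stated ±1.6 to ±2.1 is 9% to 11% too wide when the printed values are taken at face value. The pair corresponds to about 333 to 362 analysed patients across the two quantiles, or to an inflation that the plan does not describe.

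The conclusion rests on the printed SDs, independent observations and a plain 95% interval for a mean. The SD range itself comes from a cited study and was not checked. The consequence is minor: no test, decision or reported interval changes, and the sample is not too small for the stated precision unless losses exceed about 16%. It should still be corrected, because it is the only sample-size justification and appears in three places.

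**What to change.** In SAP 3.5, tie the precision to the number analysed. For example:

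> 420 patients will be enrolled. If all are analysed, the half-width of the 95% CI (Student's t) is ±1.4 for SD 15 and ±1.9 for SD 20. With about 350 Evaluable patients (about 17% not evaluable, shown for illustration) it is ±1.6 to ±2.1.

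If a loss rate, design effect or other basis was used at planning, state it and where it is recorded. If none was, keep the second scenario labelled as illustrative and do not present it as a prior assumption. Say which definition of enrolled the 420 refers to, so that any loss rate has a clear base. It would also help to note that the relevant count is valid scores per domain, since SAP 6.3.1 makes a domain invalid when more than one of its items is missing.

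Make the matching change in the current protocol versions (Spain 3.0, Italy 2.0) if they still carry this sentence.

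The cost is wording: one short paragraph in the SAP and the matching protocol sentences. Enrolment, data collection and analysis do not change. Protocol 17.2 requires amendments to be notified, so the SAP can be corrected now and the protocol text at the next amendment.

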4. DEFINITIONS AND GENERAL METHODOLOGY

4.1. General Methodology

All statistical tables, listings and analyses will be produced using SAS® release 9.4 or later (SAS Institute, Inc, Cary, NC, USA).

The data from all sites will be pooled and summarized.

Continuous data will be summarized with mean, standard deviation (SD), median, first (Q1) and third (Q3) quartiles, minimum and maximum. Categorical data will be presented by absolute and relative frequencies (n and %) or contingency tables. The percentage calculation will be based on total values (i.e., count will be shown also in the missing category, unless otherwise specified). Bilateral 95% confidence limits will be presented as appropriate. Unless stated otherwise, a two-sided alpha level 0.05 will be considered.

4.2. Definitions

Study Phases

The following phases are identifiable:

- **Screening period:** Day -28 to Day -1
Period of up to 4 weeks before Baseline used to assess patient eligibility. The screening period starts with the signing of the informed consent. No re-screening of patients is allowed.
- **Treatment period:** Day 0 (Baseline) to Day 4
This period started with the first treatment administration (Day 0) and ended at the last treatment administration planned at Day 4.
At the Baseline visit (Day 0), after confirmation of eligibility, patients will be included and treated with Tirbanibulin administered topically at a dose of 2.5 mg once daily for 5 consecutive days to a contiguous up to a 25 cm² area field on the face or scalp.
- **Follow-up period:** Day 5 to Day 57
In this period 2 visits are scheduled at Day 8 (Visit 3) and at Day 57 (Visit 4, Final Visit), but only for 1 site (i.e. Hospital Clinic de Barcelona), study visits will be held at Screening and on Day 0 (baseline), Day 8, Day 15, Day 29 and Day 57.

	
Statistical Analysis Plan

	
Sponsor: ALMIRALL, S.A.

	
Protocol number: M-14789-42

- **End of Study**

Day 57 visit (Visit 4) will constitute the End of Study Visit.

Definition of Screening Failures

Participants who sign an informed consent form and subsequently found to be ineligible (i.e., due to non-meeting of inclusion/exclusion criteria) will be considered screen failures. The reason for screen failure (i.e., protocol deviation and non-protocol deviation) will be properly summarized.

Definition of Baseline

Baseline date (Day 0) is defined as the date of the first Tirbanibulin administration, i.e., Visit 2 date.

First/Last Administration of Study Treatment

The date of first treatment administration is the first “Date of study medication application” in TIRBANIBULIN (STUDY DRUG) APPLICATION eCRF page (and it should coincide with Baseline date).

The date of last treatment administration is the “Last known date subject took study treatment” in END OF TREATMENT DISPOSITION eCRF page.

End of Trial

The “end of trial” is defined as the date when all patients complete the Day 57 visit or prematurely discontinue from the study, i.e., “Date of Discontinuation /Study completion” date in END OF STUDY DISPOSITION eCRF page.

Completed Patient

A participant is considered to have completed the study if he or she has completed all phases of the study including the last visit and the last scheduled procedure shown in the Table 1 reported in Section 2.4 of this document. Only patients who perform the last scheduled follow-up contact, i.e., who performed Visit 4 will be considered trial completers.

4.3. Coding of Therapies and Medical Terms

Medications/therapies reported in PRIOR AND CONCOMITANT MEDICATIONS/THERAPIES eCRF pages will be coded using version B3_Q1_2023 of the World Health Organization (WHO) dictionary. Medical terms reported in the MEDICAL HISTORY, SURGICAL AND MEDICAL PROCEDURES or ADVERSE EVENTS eCRF pages are coded using version ENG 26.0 of the Medical Dictionary for Regulatory Activities (MedDRA).

	
Statistical Analysis Plan

	Sponsor: ALMIRALL, S.A.
	Protocol number: M-14789-42

Versions of the dictionaries can be upgraded during the study according to Sponsor's request.

4.4. Handling of Drop-Outs or Missing Data

4.4.1. Missing or Partial Dates

No imputation of missing/partial dates will be performed.

4.4.2. Handling of Missing Data/Imputation/Censoring Rules

Patients will be included in each analysis based on available data. No replacement of missing values will be performed. In case of missing values, they will be displayed as "Missing" in the descriptive analysis.

4.4.3. Handling of Drop-Out Patients

Screening failure patients and drop-out patients will not be replaced in this study.

4.5. Multiple Comparison/Multiplicity

Not applicable.

4.6. Multicentre Studies/Center Pooling

The study will be conducted at about 33 sites in Spain and 7 sites in Italy. The data from all centers will be pooled and summarized.

5. ANALYSIS POPULATIONS

Starting from Screened patients (i.e., all patients who signed the informed consent form), the following analysis populations will be defined for statistical analysis:

- **Enrolled population:** all patients who signed the informed consent form and completed the screening disposition.
- **Full analysis set (FAS) population:** all patients who signed the informed consent form and applied at least one dose of Tirbanibulin.
- **Evaluable patient population:** FAS patients who completed the 57 days of observation and have the TSQM-9 assessment.
- **Safety patient population:** Full analysis set patients.
- **LC-OCT Population:** FAS patients who performed at least one valid LC-OCT assessment (i.e., FAS patients enrolled at site 101).

	Statistical Analysis Plan Sponsor: ALMIRALL, S.A. Protocol number: M-14789-42
---	--

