- The primary trial endpoint is Treatment Satisfaction Questionnaire for Medication Version 9 (TSQM-9) score at Day 57.

Secondary Endpoints

Patient-reported outcomes:

- Change from baseline in Skindex-16 at Day 57.
- Organoleptic properties of tirbanibulin assessed on a Likert Scale at Day 8.
- TSQM Version 1.4 (TSQM 1.4) at Day 57.
- Patient treatment preference assessed through question 1 (Q1) to question 9 (Q9) of the Expert Panel Questionnaire (EPQ) at Day 57.

Efficacy

- The percentage of patients with complete (100%) clearance of all lesions within the application area at Day 57.
- The percentage of patients with partial clearance, defined as a reduction of at least 75% in the number of lesions within the application area at Day 57.
- Number of old and new AK lesions at Day 57.
- Olsen characterization at baseline (Day 0; pre-dose) and Day 57.

Clinical Trial **M-14789-42**

Clinical Trial Protocol Version No.1.0, Date 08/05/2022

- Reflectance confocal microscopy (RCM) and optical coherence tomography (OCT) of subclinical lesions (at only one selected site: Hospital Clinic de Barcelona) at baseline (Day 0; pre-dose), Day 8, Day 15, Day 29, and Day 57.

Physician reported outcomes

- Physician outcomes assessed through question 1 (Q1) to question 10 (Q10) of the EPQ at Day 57.

Safety

- Incidence and severity of adverse events
- Incidence and severity of local skin reactions (LSRs) (erythema, flaking or scaling, crusting, swelling, vesiculation or pustulation and erosions or ulcerations at the application-site) on a grading scale ranging from 0=absent to 3=severe. Application-site reactions such as application-site pruritus and application-site pain (including pain, tenderness, stinging, and burning sensation) not classified as LSRs will be reported as adverse events (AE).

Adherence to the therapy

- Medication adherence is recorded using a self-administered Patient Diary from Day 0 to Day 4. These questions will be related to usage pattern (dosage, frequency, and site) of study medication application, adverse reactions, and reasons for any missed or delayed doses.

7 Trial Design and Rationale

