11.2 Statistical Analysis

Analysis Populations

The **Enrolled population** will consist of all patients who signed the informed consent form.

The **Full analysis set (FAS) population** will consist of all patients who signed the informed consent form and applied at least one dose of tirbanibulin.

The **Evaluable patient population** will consist of FAS patients who complete the 57 days of observation and have the TSQM-9 assessment.

The **Safety patient population** will consist of FAS patients.

The primary and secondary analyses will be done on the Evaluable patient population.

All safety outcomes and other variables (i.e., concomitant medication, number of withdrawals) will be analyzed considering the Safety Population.

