6.3. Efficacy Evaluation

6.3.1. Primary efficacy analysis

The primary efficacy analysis will be evaluated on the Evaluable population. All data collected in the database will be taken into account.

Definition of primary endpoint

The primary objective is to assess treatment satisfaction on Day 57 in patients with AK of the face or scalp following treatment with Tirbanibulin ointment 1% administered once daily for 5 consecutive days. Primary objective will be evaluated through Treatment Satisfaction Questionnaire for Medication Version 9 (TSQM-9) score.

TSQM-9 is a 9-item clinically validated psychometric instrument developed from the TSQM 1.4 (an extended version of TSQM-9 composed by 14 items more accurately described in Section 5.3.2.3 of this document): in fact, the 5 items associated with side effects related to the medication (question 4 to 8 of Version 1.4) are excluded in TSQM-9. It comprises 3 domains: efficacy (questions 1-3), convenience (questions 4-6), and global satisfaction (questions 7-9) of the drug application.

Similarly to TSQM 1.4, the TSQM-9 global total scores [1] vary from 0 to 100 with higher score indicating higher treatment satisfaction. In order to calculate the three domain scales, the responses to items will be summed and transformed. Specifically, the scores will be computed by adding the items loading on each domain. The lowest possible score (for each item the lowest possible score is 1, therefore for all the three subscale the lowest possible score is 3) will be subtracted from the composite score

	Statistical Analysis Plan Sponsor: ALMIRALL, S.A. Protocol number: M-14789-42
---	--

and divided by the greatest possible score. This will provide a transformed score between 0 and 1 that is then multiplied by 100. For a more schematic explanation, see the table below:

Score calculation formula	
Effectiveness	
If no missing item	$\frac{(\sum \text{item1, item2, item3}) - 3}{18} * 100$
If one missing item	$\frac{(\sum \text{the 2 completed items}) - 2}{12} * 100$
Convenience	
If no missing item	$\frac{(\sum \text{item4, item5, item6}) - 3}{18} * 100$
If one missing item	$\frac{(\sum \text{the 2 completed items}) - 2}{12} * 100$
Global satisfaction	
If no missing item	$\frac{(\sum \text{item7, item8, item9}) - 3}{14} * 100$
If item7 or item8 missing	$\frac{(\sum \text{the 2 completed items}) - 2}{10} * 100$

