6.3.2. Secondary efficacy analysis

The secondary efficacy analysis will be evaluated on the Evaluable population if not differently specified. All data collected in the database will be taken into account.

The secondary objective is to evaluate patient-reported outcomes, physician-reported outcomes, efficacy, and safety following treatment with Tirbanibulin ointment 1% administered once daily for 5 consecutive days.

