6.3.2.2. Likert Scale for organoleptic properties of Tirbanibulin

Definition

Likert scale is an instrument used to measure the individual's degree of agreement and disagreement with a variety of statements about some attitude, options, or their

	
Statistical Analysis Plan

	
Sponsor: ALMIRALL, S.A.

	
Protocol number: M-14789-42

feelings. In this study, the product's organoleptic properties are evaluated with Likert scale. The questionnaire is built with questions related to the product's characteristics namely appearance, color, convenience, texture, smell, and the feelings experienced during drug application. The Likert scale offers 7 possible answers, from "totally agree" to "totally in disagreement".

In this secondary objective the main purpose is the description of organoleptic properties (i.e appearance, color, convenience, texture, smell, and the feelings experienced during drug application) of Tirbanibulin through the Likert Scale at Day 8.

Analysis methodology

The number and percentages of patients who completed the questionnaire at Day 8 (i.e. Visit 3) will be summarized.

Scores of each question obtained by patients will be summarized with descriptive statistics and 95% CI (calculated for the multinomial proportion) of each question' response will be provided. In case the lower limit of CI is negative due to small frequency of the category, 0 will be imputed as lower limit.

Data handling rules

No missing imputation will be performed.

Sensitivity of secondary analysis

Not applicable.

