6.3.2.5. AK lesions characteristics

Definition

For each patient the following assessments (reported in AK LESION COUNT and in AK LESION COUNT AND OLSEN GRADING eCRF pages) will be provided:

- Presence of AK lesions (counted only if they are inside the treatment area) at Screening and Baseline and count of new and old AK lesions ad Day 57
- Reduction of number of lesions at Day 57 will be calculated considering only old lesions as:

	
Statistical Analysis Plan
 
Sponsor: ALMIRALL, S.A.
 
Protocol number: M-14789-42

---	---

$$\frac{N. \text{ lesions at Baseline} - N. \text{ old lesions at Day 57}}{N. \text{ lesions at Baseline}} * 100\%$$

N. old lesions at day 57 is reported in AK LESION COUNT AND OLSEN GRADING eCRF page.

- Reduction of number of lesions at Day 57 will be calculated considering considering both old and new lesions, as:

$$\frac{N. \text{ lesions at Baseline} - N. \text{ lesions at Day 57}}{N. \text{ lesions at Baseline}} * 100\%$$

Where, N. lesions at day 57 = N. new lesions + N. old lesions reported in AK LESION COUNT AND OLSEN GRADING eCRF page.

- Occurrence of complete clearance of all AK lesions within the application area, is defined as a reduction from baseline in the number of lesions = 100% at day 57
- Occurrence of partial clearance is defined as a reduction $\geq 75\%$ in the number of lesions within the application area at Day 57.

Analysis methodology

All the analysis reported in this section will be provided by country, AK lesion localization and overall.

The number and percentages of patients who performed the AK lesions count at each timepoint (i.e., Screening Visit, Baseline Visit and Final Visit) will be reported.

The number of the AK lesions at Screening, Baseline and Final Visit (new, old and total AK lesions) will be provided.

The change from Baseline Visit of the AK lesions count will be described at Final Visit reporting also the corresponding 95% CI estimated by Student's t distribution, regardless response's distribution.

The number and percentages of patients with a complete clearance will be provided with the corresponding 95% CI calculated with the Binomial exact method.

	
Statistical Analysis Plan
 
Sponsor: ALMIRALL, S.A.
 
Protocol number: M-14789-42

---	---

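### Secondary efficacy endpoints other than LC-OCT are confined to Day 57 completers with a TSQM-9, so the Day 8 rating depends on a later event, clearance has no FAS estimate, and the set's definition and exclusion table disagree

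*SAP*

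**What the plan says.** The Evaluable set is defined in SAP section 5 as "FAS patients who completed the 57 days of observation and have the TSQM-9 assessment". Protocol 11.2 states: "The primary and secondary analyses will be done on the Evaluable patient population". SAP 6.3.1 applies the set to the primary endpoint ("The primary efficacy analysis will be evaluated on the Evaluable population"). SAP 6.3.2 makes it the default for the rest: "The secondary efficacy analysis will be evaluated on the Evaluable population if not differently specified".

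That wording leaves room for exceptions, but SAP 6.3.2.1 to 6.3.2.6 (Skindex-16, Likert, TSQM 1.4, EPQ, lesion counts and clearance, Olsen) name no other set. Only LC-OCT has its own population. Outside safety, the FAS is used for demographic and baseline tables (SAP 6.2).

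The endpoints concerned include:
- Protocol section 6: "Organoleptic properties of tirbanibulin assessed on a Likert Scale at Day 8". SAP 6.3.2.2 adds: "The number and percentages of patients who completed the questionnaire at Day 8 (i.e. Visit 3) will be summarized".
- SAP 6.3.2.5: "The number and percentages of patients with a complete clearance will be provided with the corresponding 95% CI calculated with the Binomial exact method". Partial clearance is handled in the same way. The sensitivity entry for this section is given as not applicable.

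On missing data, SAP 4.4.2 says "Patients will be included in each analysis based on available data" and rules out replacing missing values. Protocol 11.5 also rules out imputation. Drop-outs are not replaced (Protocol 11.1, SAP 4.4.3).

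**The concern.** The secondary objective is to describe outcomes following treatment, which points to the treated patients. The default set selects instead on two events at the end of follow-up.

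- **Day 8 Likert.** The rating needs neither event. A patient who rated the ointment at Day 8 and then left the study is removed, and neither document gives a reason.
- **Day 57 lesion count, Olsen grade and both EPQ versions.** These need the Day 57 visit but not the TSQM-9. The clinician EPQ is even in a separate booklet (Protocol 12.1.5).
- **Clearance.** A completer rate can differ from the rate in all treated patients if leaving the study is related to outcome. Protocol version 1.0 has two such exits: withdrawal on starting systemic or topical AK therapy (9.6.3), and disease progression among the reasons for discontinuation or withdrawal (8.5). No FAS figure is planned that would show how far the result depends on who stayed.

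**Working it through.** **1. Which patients are in the set.** Consider a treated patient who attends Visit 4, has a lesion count, Olsen grade and clinician EPQ, but has no TSQM-9.
- SAP section 5 definition: outside the Evaluable set, because a TSQM-9 is required.
- SAP 6.1, Table 5.1-1: the coded exclusions from the Evaluable set are no application of study drug (NOPD01) and discontinuation before Visit 4 (NOPD02). Neither applies, so the patient stays in.

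The two rules give different sets for the same patient. Such patients should be few, because the patient booklet is completed at the visit under supervision (Protocol 12.1.4).

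**2. The plan's own precision figure.** The documents give no precision for clearance. The only stated figure is a half-width of 1.6 to 2.1 for a TSQM-9 component mean, with N = 420 and SD 15 to 20. The formula 1.96 × SD / √n gives 1.96 × 15 / √420 = 1.43 and 1.96 × 20 / √420 = 1.91, so the stated figure is not reproduced. Both stated values are recovered after rounding only for n = 333 to 359. This does not decide the present point.

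**3. Bound for clearance.** Inputs:
- 420 treated patients (planned enrolment).
- Loss from the Evaluable set of 5% (21) or 10% (42). This is an assumption; the documents state no rate.
- Complete clearance of 44%, 54% or 68%. Protocol 5.1.4 and 5.2 agree on 44% for the first phase 3 trial but disagree on the second (68% against 54%), so all three are run.

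With n evaluable patients and x of them cleared, the completer rate is x/n, with an exact binomial 95% CI as in SAP 6.3.2.5. The FAS worst case is x/420 and the best case is (x + lost)/420.

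| Lost | Completer rate (95% CI) | FAS, lost = not cleared | Drop (points) | FAS, lost = cleared |
|---|---|---|---|---|
| 21 | 176/399 = 44.1% (39.2–49.1) | 176/420 = 41.9% | 2.2 | 197/420 = 46.9% |
| 21 | 215/399 = 53.9% (48.9–58.9) | 215/420 = 51.2% | 2.7 | 236/420 = 56.2% |
| 21 | 271/399 = 67.9% (63.1–72.5) | 271/420 = 64.5% | 3.4 | 292/420 = 69.5% |
| 42 | 166/378 = 43.9% (38.8–49.1) | 166/420 = 39.5% | 4.4 | 208/420 = 49.5% |
| 42 | 204/378 = 54.0% (48.8–59.1) | 204/420 = 48.6% | 5.4 | 246/420 = 58.6% |
| 42 | 257/378 = 68.0% (63.0–72.7) | 257/420 = 61.2% | 6.8 | 299/420 = 71.2% |

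At 5% lost, every worst case lies inside the completer CI. At 10%, it is inside for 44%, just below the lower limit for 54% (48.6 against 48.8) and clearly below for 68% (61.2 against 63.0). The lower limit is first reached at 49 lost (49/420 = 11.7%) for 44% and at 31 lost (31/420 = 7.4%) for 68%.

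For partial clearance (protocol figures from 54% to 76%) the drop is 2.7 to 3.8 points at 5% lost and 5.4 to 7.6 at 10%. At 76%: 303/399 = 75.9% against 303/420 = 72.1%, and 287/378 = 75.9% against 287/420 = 68.3%.

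No comparable bound is offered for the Likert items, because the documents give no expected values for them.

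**The case against.** The best defence is that the set is prespecified, that Protocol and SAP agree on it, and that the study is single-arm and descriptive with clearance as a secondary endpoint. All of this is true. The point is therefore a weakness in the choice of analysis set, not a conflict between the two documents.

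Some stronger readings are tempting, and the documents do not support them.

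- *SAP 4.4.2 contradicts the Evaluable set.* It governs missing values and does not override a set named elsewhere.
- *Observed Day 57 data will be dropped unseen.* Whether they are dropped depends on which rule in step 1 is applied. SAP 6.1 also plans completer counts, population sizes and reasons for exclusion, so the number excluded could be worked out.
- *None of these endpoints needs either condition.* That is strictly true only of the Day 8 Likert and the baseline Olsen grade.
- *The stated TSQM-9 precision reveals an expected loss of 61 to 87 patients (420 − 359 to 420 − 333).* No drop-out allowance is stated, so this is a guess.

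Two further objections stand. The exit rules come from Protocol version 1.0, whereas the SAP follows version 3.0 (Spain) and 2.0 (Italy), which were not available; SAP 3.3.3 repeats the prohibition on other AK treatment of the treated area but not the withdrawal. And counting a missing lesion count as not cleared is a form of imputation, which the plan excludes, so it can only be supplementary.

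**Conclusion.** The concern holds on the SAP text. The Day 8 Likert endpoint is conditioned on a later event without a stated reason, the SAP 5 definition and Table 5.1-1 must be reconciled, and clearance has no FAS estimate.

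A reader might infer that the planned clearance rates are overstated by several points. The documents do not show that. Upward bias is plausible given the exit rules in version 1.0, but its direction and size are unknown without a drop-out rate. The table gives bounds under assumed losses of 5% and 10% of 420, with every lost patient counted as a failure. On that footing the effect on complete clearance is minor at 5% and about one CI half-width (5 points) at 10%. The change is worth making because it is cheap and the documents cannot show that the effect is negligible. The primary TSQM-9 analysis is not in question.

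**What to change.** Record the changes in SAP 1.1.

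1. In SAP 6.3.2.2, analyse the Day 8 Likert data in all FAS patients with Day 8 data. In 6.3.2.4 to 6.3.2.6, analyse both EPQ versions, lesion counts and Olsen grade in all FAS patients with that assessment, without requiring a TSQM-9.
2. In SAP 6.3.2.5, keep the Evaluable clearance result and place beside it a supplementary FAS table for complete and partial clearance, with a missing Day 57 count treated as not cleared, plus the best-case and worst-case range. Label it a sensitivity analysis that departs from the no-imputation rule and was added after the interim analysis (SAP 6.6).
3. Reconcile the SAP 5 definition with Table 5.1-1, for example by adding a code for a missing TSQM-9.

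The cost is SAP wording and a few more tables from data already collected. The downside is that denominators will differ by endpoint and the FAS clearance figure will be equal to or below the Evaluable one, by more as drop-out rises.
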